3.4 Recruitment

Promotional material to make potential participants aware of the research will be displayed in the waiting areas of the Emergency Department (ED). This material will be in place only during the weeks of data collection and emphasises that the study is not only investigating patients with a specific condition (such as alcohol dependence).

A copy of a poster is included within the Appendix (Poster v2.6). Promotional material is only being used to raise awareness of the existence of the study and informed consent will be obtained separately by the research staff.

Potential participants will first be assessed by clinical research staff to ensure they are appropriate to approach. In cases of doubt the clinical research staff will consult senior ED staff. The research team will also ask the clinical team to signpost the existence of a research study to patients if possible. Potential participants will then be approached by the research staff, given an information leaflet to explain the purpose of the study and will be given a verbal explanation of the study's aims, what participation involves and invited to ask any questions they have about the study. Patients will be asked if they would like more time to consider whether they wish to participate and if so, the research nurse will re-approach the potential participant at a later time.

Attempts will be made to brief ED staff about the study (including at continuing professional development sessions and handover periods). ED staff will be encouraged to mention the existence of the study to patients but ED staff are unlikely to have the available time to fully brief patients about the nature of the study and hence will not be responsible for obtaining informed consent.

Participants will be provided with as long as they require during their current attendance at the Emergency Department (ED) to consider whether to participate. Given that participant involvement involves completion of a short questionnaire only, it is envisaged that a proportion of patients would prefer to take part immediately following their approach. While this will be allowable, research staff will ensure that participation is fully informed prior to obtaining written consent. In particular, a low threshold will be maintained for the research staff providing time to reflect on participation and for research staff coming back at a later time. Coenrolment, for patients also involved in other studies, will be acceptable.

Study involvement is envisaged to last 5-10 minutes of active participation for each patient involved. However, we envisage that some patients may require a greater length of time than this. To allow this, at least two research nurses will be responsible for data collection at each

shift so that adequate time is available to allow data collection from willing participants and ensure adequate time for patients to reflect on whether they wish to participate.

Research staff will emphasise that participation is entirely voluntary (with clinical care being unaffected by their decision to participate or otherwise), they are free to withdraw at any stage of data collection if they do decide to participate and that further information on their clinical outcomes will be sought from their clinical notes. Research staff will explain that all information will be kept strictly confidential and all identifiable information will be removed prior to data analysis. In addition, it will be emphasised that no information provided by patients to research staff will be recorded in ED notes or shared with ED personnel but is for research purposes only.

Informed consent will be required from all participants who take part in the face-to-face survey. This will be documented using a paper form (MUP ED Participant Consent Form v2.5). During the consent process, researchers will also seek consent for linkage to administrative health data (including Scottish Morbidity Records in Scotland and Hospital Episode Statistics in England). It will be emphasised that it is not necessary to agree to this process to take part in the study, data linkage will be carried out confidentially by NHS staff and they can withdraw from this component of the study at a future time if they wish to. The process for withdrawal will be explained (via an online form on the study website, via a telephone call or by email). This information will be included on the information leaflet and the location of this information will be indicated to participants. Again, research staff will emphasise the voluntary nature of data linkage.

Interpreter services will be used to provide information to potential participants who are not able to speak English if available at the time of approach. If it is unclear whether the participant has understood the information provided, the recruitment attempt will be excluded. Similarly, if no suitable interpreters are available, the patient will be excluded from the study. Given the nature of the questions asked, family members will not be used for interpretation purposes. Written translations of the information leaflet for a number of languages (Mandarin, Hindi, Polish) will be available for the main study but not for the pilot phases. Information included in the information leaflet will be verbally reviewed by the research staff with the patient.

3.5 Withdrawal and loss to follow up

If the participant loses capacity to consent during the process of data collection, their research data would be withdrawn from the study. As active involvement is relatively short, occurrences of this type of event are expected to be rare.

We will not be planning to re-contact participants after their involvement in the study. This is to ensure that their participation (including attendance at the Emergency Department) in the study can be kept confidential. However, we plan to make a plain language version of the study results available on the study website. A link to the study website will be included on the participant information leaflet and participants will be informed that results will be available from that source. In addition, we plan to work extensively to disseminate the results of the study to the general public through the mass media.

For participants who have provided consent for data linkage, they will have the opportunity to withdraw their consent by contacting the study team. Contact details and information on this process will be included within the Participant Information Leaflet.

3.6 Study Procedures

Prior to the main study data collection, two pilot phases of research are planned. Data collection for the first pilot phase will occur for one day shift and one night shift with two research nurses (with honorary or substantive NHS contracts) being responsible for data collection for each shift. This pilot phase will help the research team to ensure data collection instruments are appropriate and identify any unexpected barriers to smooth conduct of the research. To achieve this, additional open-ended questions will be asked for a small subset of participants (see Interview Schedule for Pilot Phase v2.5 and Qualitative Interview for Pilot Phase Consent Form v2.5). Approximately 10-15 patients (purposively sampling for patients who have refused to take part in the main study (if possible), agreed to take part in some but not all aspects of the main study and agreed to take part in all aspects of the main study) will be interviewed in a short one-to-one qualitative interview. Diversity in age group, socioeconomic position and gender will also be sought. If following the pilot work, the research methods for further phases of the study require modification, an amendment or further application to the research ethics committee will be made as appropriate. We anticipate that further pilots would be beneficial in this phase, prior to the first wave of data collection in February. This will allow us to do more testing and refinement of the data collection processes to maximise response rate.

A second pilot phase is planned in the run-up to the first wave of the main study. This will be conducted across all four sites and will help ensure that the research staff do not interfere with the smooth operation of the ED. Identical data collection procedures for all of the above phases are planned (with modifications requiring further applications or amendments to the research ethics committee). During data collection, clinical research staff will identify patients who are not appropriate to be approached for participation in the study and should be excluded, and in cases of doubt senior clinical ED staff will be consulted. Research staff will approach all patients who are not considered inappropriate to approach.

Research staff will receive in-depth training from the research team and others, with half-day training on issues related to obtaining informed consent planned. This training will be delivered by a professional with a high level of expertise in relation to the clinical care of people with addiction (e.g. [name], Professor of Addiction Psychiatry and Consultant Psychiatrist). It will include information on the potential for fluctuating consent and raise awareness of specific pathologies that may impede informed consent (e.g. Korsakoff's syndrome). Research staff will also be trained to provide contact details to existing facilities for assistance on issues related to alcohol use, drug use and domestic abuse, for participants who request it. Contact details for further information on alcohol issues (available from Drinkline) will be included at the end of the participant information leaflet so that all those approached can seek further information and help if they wish to do so.

3.7 Data Collection

Each wave will collect data over three weeks, ideally with one wave of data collection prior to the implementation of MUP and two post-implementation waves (after six months and 12 months). To maximise collection of both alcohol-related attendances and hazardous drinkers, data collection will occur from 2000 to 0400 on Thursday to Sunday (i.e. 32 hours per week during this time period) and 0900-1700 on Monday to Wednesday (i.e. 24 hours per week during this time period). If deemed necessary by local sites, different 8 hour timeslots will be considered, to meet local attendance patterns. As noted above, periods of the year when alcohol consumption is atypical will be avoided.

Patients will be approached by research staff to seek permission to complete a short face-to-face interview. The reasons for exclusion will be recorded electronically on the iPad along with 5 year age group and sex. Excluded patients will not be assigned a study ID and so will be completely anonymous.

All suitable patients will be approached, their eligibility confirmed, and, if eligible, informed consent will be sought and a face-to-face interview administered, based on a previously used patient questionnaire [36]. Research nurses will be responsible for obtaining written informed consent, completing the data linkage form if consent has been obtained -and then proceeding to conduct the face-to-face survey. These will all be electronic documents contained on an iPAD.

The face-to-face survey will collect information on socio-demographic details, problematic alcohol use (FAST Alcohol Screening Test), alcohol consumption in the last 24 hours, self-assessment of whether alcohol contributed to the attendance and self-report of whether the patient has been a victim of violence. Research nurses will input the information into the standardised electronic form which will include a number of options to assist with timely completion. Paper versions of the survey, and consent and linkage forms are enclosed (ED Survey v2.5). The Interview Schedule for Pilot Phase v2.5 and Qualitative Interview for Pilot Phase will be on paper only. Back up paper copies of all electronic documents will be available in case of iPad failure. An ED attendance database will be maintained for all attendances during data collection periods to allow monitoring of patient recruitment.

Research staff will retrieve additional data on participants from patient records, either during data collection sessions (if time allows), or at a later time. The following information will be sought from the clinical records:

- demographic characteristics (date of birth, sex, postcode),
- attendance details (time, triage category),
- discharge status
- diagnoses at discharge (coded by ICD10 categories) and all relevant data relating to reason for admission and diagnosis (whether ICD10 or another coding system or free text).

We will calculate the consent rate among those eligible. However we need to assess the representativeness of the interviewees and attendees in the study timeslots, and the certainty of our estimates of the proportion of attendances that are alcohol-related. To make this possible, we propose to request from hospital records anonymised information on all attendees over the three week data collection periods for each wave. We wish to ask for 5 year age groups, sex, reason for attendance, and other relevant data for diagnosis (whether ICD10 or another coding system or free text). We will request that attendees within the timeslots for the study are flagged, so that we can calculate a true recruitment rate for those interviewed and for whom we have reasons for exclusion.

Data collection will be conducted by Clinical Research Facilities (CRFs), on behalf of the study team. Each CRF will be responsible for ensuring line management of their staff, as per their usual operating procedures. The research nurses responsible for data collection will have received training, with training available for additional research nurses (to allow for rota gaps to be filled, in the event of illness etc.). It is recommended that any data collection session should include at least one more experienced research nurse, so that more junior research nurses feel adequately supported. Research nurses will be able to contact a member of the study team throughout data collection periods in the event of an emergency.

The study will be coordinated by a project coordinator based at the SPHSU who in turn will be supported by a post-doctoral researcher. These individuals will be responsible for ensuring distribution of materials for data collection to the sites and liaising with CRF staff to coordinate the study and in particular, ensure that data collection processes are followed consistently across sites and over time. During each wave of data collection, all paper-based forms should be stored securely using existing CRF facilities, with any data linkage forms stored separately from

consent forms. Consent forms, should be returned to the SPHSU using secure couriers at the end of each three week data collection period. It is the responsibility of the project coordinator to monitor transfers of the data and consent forms to the SPHSU. All electronic survey and linkage data will be sent through electronic secure transfers to the SPHSU server. This approach has been previously applied by members of the study team for randomised controlled trials conducted within the ED setting.

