3.3 Participant Selection

The target population for the study is all patients over 16 years age who attend EDs to receive acute treatment for a health condition.

The exclusion criteria for the sample are used to decide whether to approach patients and having approached whether the patient is eligible:

Deemed clinically inappropriate to be approached.

- 'patient too unwell',
- · too distressed,
- grossly intoxicated (alcohol),
- grossly intoxicated (drugs)
- Cognitive impairment
- · Police in attendance,
- Clear language barrier, and no interpreter available
- · Patient already participating,
- routine follow up that has been instigated by ED staff,
- Patient left dept
- Patient admitted,
- staff safety issue,
- End of shift,
- dead on arrival,
- other.

For those who are approached, the inclusion criteria are:

- >=age16
- able to speak English and no interpreter available.
- Is a new ED presentation,
- The patient is conscious
- The patient is physically well enough
- The patient is mentally well enough
- The patient is sober enough (alcohol)
- The patient is sober enough (drugs)
- The patient is still in the department
- The patient is safe for staff to approach

During data collection periods, an ED attendance database will be maintained for all attendances to allow monitoring of patient recruitment. This will help prevent patients being approached on multiple occasions. This attendance database will be destroyed at the end of each recruitment shift. In addition, data on sex, five year age group and diagnoses for all attendees in all the three week waves, with the attendees within the study timeslots flagged, will be requested from hospital records. This is to enable the assessment of the representativeness of our sample and of our estimates of the proportion of alcohol-related attendances.

We intend to obtain a total sample size of at least 2820 participants across all four sites over each three week period of data collection. This equates to 235 participants per week per site of data collection. No target sample size is required for the pilot phases of the study as these phases are intended to help identify potential practical issues involved in conducting the study.

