3.8 Data Analysis

Primary outcome

The primary outcome will be changes in absolute numbers of alcohol-related attendances as defined by any one of:

- patient self-reports attendance is alcohol-related
- patient reports alcohol consumption in past 24 hours of ≥8units in men or ≥6 units in women
- patient not approached because too intoxicated with alcohol

Secondary outcomes

Secondary outcomes will be changes in:

- absolute number of alcohol-related attendances by age/sex/deprivation
- problematic alcohol use (as defined by the Fast Alcohol Screening Test (FAST))
- mean FAST score
- prevalence of binge drinking in the past week
- reason for attendance (coded by ICD10)

After the first post-intervention wave, we will test for differences in the outcomes between the intervention and comparison groups using a fixed-effects regression model, with individuals nested within EDs, before and after adjustment for relevant covariates including baseline levels of alcohol-related attendance, demography, triage category etc. We will also attempt to determine the nature of the effect more precisely in terms of whether a dose-response effect according to the time since MUP was implemented (through a test of the significance of an interaction between time and intervention). We will test for interactions of the intervention with defined important covariates (including age, gender, deprivation quintile, disease diagnostic categories) to investigate the possibility of differential intervention effects and will subsequently stratify the analyses if indicated.

4. Research Governance and Regulatory Issues

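### Patients too intoxicated to approach count in the primary outcome but cannot enter its triage-adjusted, by-deprivation or by-diagnosis analyses

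*Protocol*

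**What the plan says.** Protocol section 3.8 defines an alcohol-related attendance by any one of three components. Two come from the interview: self-report that the attendance is alcohol-related, and units drunk in the past 24 hours. The third is "patient not approached because too intoxicated with alcohol". Section 3.3 lists gross alcohol intoxication among the reasons for exclusion, so this third group is never interviewed.

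For excluded patients, section 3.7 says: "The reasons for exclusion will be recorded electronically on the iPad along with 5 year age group and sex". It continues: "Excluded patients will not be assigned a study ID and so will be completely anonymous".

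Other data come from three places:

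- **Clinical records.** "Research staff will retrieve additional data on participants from patient records" (section 3.7). Postcode, triage category and discharge diagnosis are on that list.
- **Anonymised hospital extract on all attendees** (sections 3.3 and 3.7). This covers age group, sex, reason for attendance and diagnosis, with study timeslots flagged. Triage category and postcode are not listed.
- **ED attendance database.** "This attendance database will be destroyed at the end of each recruitment shift" (section 3.3).

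Section 3.8 then plans a regression, reported unadjusted and adjusted for "relevant covariates including baseline levels of alcohol-related attendance, demography, triage category etc". It also plans a secondary outcome, "absolute number of alcohol-related attendances by age/sex/deprivation", and interaction tests that include deprivation quintile and diagnostic category.

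**The concern.** One component of the primary outcome consists of people for whom the protocol collects almost no covariates. A regression that uses triage category or deprivation quintile has no value to enter for them. Every such record is an event by definition, so losing them is selection on the outcome.

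Two things are at stake. First, the unadjusted estimate would rest on three components and the triage-adjusted estimate on two. A reader would take any difference between them for control of confounding. Second, research objective 2c (deprivation) would be answered without the most intoxicated attenders, and nothing in the text says so.

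**Working it through.** **Which analyses can hold these patients**

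| Analysis in section 3.8 | Field needed | Available for the too-intoxicated? |
|---|---|---|
| Unadjusted primary outcome | exclusion reason | yes |
| By age group, by sex | age group, sex | yes |
| Overall distribution of reason for attendance | diagnosis or reason | yes, through the all-attendee extract |
| Triage-adjusted model | triage category | no |
| Outcome by deprivation | postcode | no |
| Composite outcome by diagnosis | diagnosis joined to outcome status | no |

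The last row fails although the extract holds diagnoses. The extract is anonymised, the exclusion log has no ID, and the attendance database is gone after each shift. No key therefore shows which extract record is a too-intoxicated case.

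**The plan's own figure.** Section 3.3 gives power above 80% for 30% against 25%. For two groups of n at two-sided 5%, power = Φ[(0.05 − 1.96·√(2·0.275·0.725/n)) / √((0.30·0.70 + 0.25·0.75)/n)]. With n = 2820 this is 98.8%. With n = 1410 (2820/2, the two Scottish sites) it is 84.5%. The stated figure is met for a simple before-after comparison, and the point here does not turn on it.

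**What losing the third component can do to the estimate.** The rates of 30% and 25% come from section 3.3. The share f of pre-MUP events that are too intoxicated is not in the documents, so 10%, 20% and 30% are assumed. England is taken as unchanged in both rate and share. I work per 100 counted attendances in the Scottish sites, so the sample size cancels.

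- All counted patients: 30 events and 70 non-events before, 25 and 75 after. Odds ratio = (25/75)/(30/70) = 0.78.
- Interviewed patients only: the non-events stay at 70 and 75, and only interviewed events remain.

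For f = 20%, the 30 events before MUP are 6 too intoxicated and 24 interviewed:

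- Fall wholly among the too-intoxicated (6 to 1; interviewed stay at 24): (24/75)/(24/70) = 0.93.
- Fall wholly among the interviewed (24 to 19): (19/75)/(24/70) = 0.74.
- Equal share in both waves (20 interviewed events after): (20/75)/(24/70) = 0.78.

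| Assumed f | Fall among too-intoxicated | Fall among interviewed | Equal share |
|---|---|---|---|
| 10% | 0.86* | 0.76 | 0.78 |
| 20% | 0.93 | 0.74 | 0.78 |
| 30% | 0.93 | 0.71 | 0.78 |

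*At 10% only 3 of the 5 points can come from the too-intoxicated; the other 2 are taken from the interviewed.

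The primary outcome is worded as absolute numbers. On that scale, at f = 20%, the ratio of event counts is 25/30 = 0.83 for everyone counted. Among the interviewed it is 24/24 = 1.00, 19/24 = 0.79 and 20/24 = 0.83 in the same three cases.

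**The case against.** The strongest reply is that little of the primary result is touched. The unadjusted comparison is planned and uses every counted patient, and age and sex are logged, so those subgroup analyses are complete. The covariate list in section 3.8 is illustrative, and the final covariate set and the handling of missing values commonly belong in a SAP. All of this is fair and limits the point. It does not remove it: the protocol names triage category and deprivation itself, and no SAP can supply fields that were never collected. A missing-triage category would not help, because that category would consist of events by definition. Imputation would rest on an assumption that cannot be tested.

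Some stronger readings are tempting but not supported:

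- A reader might infer that every diagnosis analysis loses these patients. The all-attendee extract holds their diagnoses, so only analyses of the composite outcome by diagnosis lose them.
- A reader might infer a specific, large fraction of events lost. That needs the too-intoxicated share of attendances, which is not given. It also needs the fraction of the other attenders interviewed, and the 50% in section 3.3 is a minimum among eligible attendees only. In any case, events lost are not a measure of bias, as the equal-share column shows.
- A reader might infer a loss of power. The planned 2820 per wave are participants and excluded patients come on top, so an interviewed-only model keeps its planned size.
- A reader might infer that triage adjustment also removes part of the MUP effect. Nothing in the protocol indicates that MUP alters triage category.

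**Conclusion.** The conflict between sections 3.3, 3.7 and 3.8 stands. The triage-adjusted model, the outcome by deprivation and the composite outcome by diagnosis cannot be carried out on the primary outcome as defined. The unadjusted, age and sex results are not affected.

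As an estimate of the effect on the three-component outcome, the triage-adjusted result is biased only if the too-intoxicated share changes differently between waves or countries. In the illustration it then lies between 0.71 and 0.93, against 0.78 with everyone counted. With an equal share there is no bias in the odds ratio. These figures rest on assumed shares, on an unchanged England, and on records with missing covariates being dropped. They show direction and possible size and do not predict the result. The mismatch between the unadjusted and adjusted outcomes does not depend on them.

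**What to change.** 1. Restrict the main adjusted model to covariates known for everyone counted: ED, wave, shift, 5-year age group and sex. Confirm that each exclusion entry carries site and shift, which section 3.7 does not list as fields.
2. Move triage adjustment to a sensitivity analysis labelled as interviewed patients only, and set it beside an unadjusted estimate in the same patients so that the two are comparable.
3. Define the deprivation analysis and any composite-by-diagnosis analysis as the two-component outcome in interviewed patients, in all waves and both countries.
4. As an alternative to item 3 for deprivation, and to recover triage adjustment, log triage category and deprivation quintile anonymously for this exclusion reason, if ethics approval allows. Diagnosis would need a broad diagnostic group as well. This should start at baseline: nothing can be recovered after a shift, and a later start would make the waves inconsistent.

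Items 1 to 3 cost wording only. Their price is a narrower, openly stated outcome in those analyses and a main model without triage. Item 4 costs more than wording. It needs approval for data on patients who have not consented and whom the protocol keeps anonymous, and a deprivation quintile requires looking up a postcode during the shift.
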